Intervention: *Messy Memories* is a mobile application that allows users to self-administer exposure therapy techniques outside of the traditional psychotherapy context. The intervention was initially released in a written format for individual self-help, but with the widespread use of smartphones, a mobile version was developed with the potential to further reduce barriers and increase access to mental health care. **Appendix A** shows screenshots of the user view of the various application modules. Please note that these images are only examples of the user interface and do not include every screen the user might see while interacting with the app.

Participants will be asked to engage with the *Messy Memories* application at least 3 days a week for at least 10 minutes each day using their own mobile smartphone device. Participants may proceed through the modules of the application at their own pace and may return to any module as many times as they desire throughout the 6-week intervention period. Mechanistic target and clinical symptom assessments will occur at Week 0 (baseline), Week 3 (mid-intervention), Week 6 (end of intervention), and Week 12 (follow-up). All study procedures, including eligibility screening, consent process, outcome assessments, and exit surveys, will be conducted remotely via telephone or Zoom video conference.

Modules:

- **Introduction:** Provides a general overview of the application, offers suggestions for its use, describes how stress may impact mental health, and explains how processing difficult memories related to stress may help to improve well-being.
- **Memory Processing:** Participants recall a difficult (“messy”) memory, which they will be asked to audio record, including what they did, felt, thought, smelled, saw, etc. They are then asked questions about what it was like to re-experience the memory, such as what emotions were elicited (e.g., sadness, anger, fear). Next, participants are asked to process what the memory means to them. They are then instructed to listen to their recording of the memory or re-record it as often as they like, until the memory becomes easier to re-

experience. They respond to processing questions each time they listen to or re-record their prior difficult memory.

- **Feedback:** Shows data from the participant's engagement with the application, including feedback related to memory processing.

Data collected:

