Aim 3 (exploratory): Assess engagement of the mechanistic target (PTSD symptoms) by the mobile application-based exposure therapy intervention (*Messy Memories*). **Hypothesis:** Participants will report improvement in PTSD symptoms based on pre-/post-intervention decrease in scores on the PTSD Checklist for the Diagnostic and Statistical Manual of Mental Disorders, 5th Edition (PCL-5).

Statistical approach for Aim 3: We will assess whether the *Messy Memories* intervention engages the mechanistic target (PTSD symptoms) by comparing pre-/post-intervention change in PCL-5 score using one-sample t-tests with comparison values of 0 (i.e., all null hypotheses entail no change in PCL-5 score). Given the exploratory nature of Aim 3, we will focus the interpretation of these analyses on effect sizes (Cohen's D) rather than statistical significance to assess potential signals for intervention effects.

Sample size and power estimates: Because the proposed study is a pilot trial, we did not conduct a formal power analysis. We aim to recruit as many participants as possible but selected a minimum n=30 based on pragmatics, the needs of the trial, and previous pilot studies suggesting that this sample size is sufficient to provide an accurate indication of the feasibility and acceptability of the study procedures.

Interim analyses: Given the relatively small sample size of this study and the expected minimal risk of the intervention, no interim analyses are currently planned. However, if concerns arise related to adverse events, then an interim analysis may be conducted and the study may be stopped early depending on the recommendations of the IRB and/or NIA.

Subgroup analyses: Given that this is a stage 1A/1B pilot feasibility study, we do not plan to conduct any pre-specified subgroup analyses.

4. Study Procedures

Provide a detailed description of which procedures are being conducted by Columbia researchers. You may include information about study instruments and study measures.

Recruitment: We aim to enroll ≥ 30 participants in this pilot study. Potential participants will be identified and recruited using several different approaches, each of which is described below.

1. Post-ICU support groups

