Screening: Upon granting consent to be screened, participants will be asked to complete a brief screening questionnaire (either online or over the phone with the study team) to determine their eligibility for study participation. Individuals completing the screener via Qualtrics will be asked to share their name and contact information so that a study team member can contact them if they screen eligible, if their screener is incomplete or needs clarification, or if they agree to be contacted about future research studies. All participants will be informed of their screening status upon completion of the screener. Those who do not meet study criteria will be thanked for their time and informed that they are not eligible for the study. Those who do meet study criteria will be informed that they are eligible for the study. All individuals who complete the study screener will be surveyed for interest in being contacted for future research studies and/or to provide feedback on the design of research studies.

Potential participants will be asked to report their age (those ages 18 years or older will be eligible to participate) and primary language (those able to speak and write in English will be eligible to participate). Additional sociodemographic information (e.g., sex assigned at birth, gender identity, race, ethnicity, living situation, annual household income, occupation, highest level of education, zip code, health insurance status, marital and partner status) will be collected as part of screening. Potential participants will be asked to report the approximate date of their ICU discharge (those discharged at least 30 days prior to the time of screening will be eligible to participate). Potential participants will be asked to confirm that they have access to both the internet (e.g., Wi-Fi) and to an internet-equipped smartphone device (e.g., iPhone, Android). Potential participants will also be asked to complete the PCL-5 as part of the screening questionnaire (scores ≥ 10 points are required for study eligibility). Potential participants will also be asked whether they have any physical, psychological, or cognitive condition (e.g., severe dementia, severe mental illness, severe alcohol and/or substance abuse) that would preclude them from completing any aspect of the study protocol.

In all cases, the screening consent process and responding to screening questions is expected to take approximately 25 minutes to complete.

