Consent: Individuals who are screened and found to be eligible for the study based on inclusion and exclusion criteria will then be invited to schedule a visit (either by phone or Zoom, depending upon the participant's preference) to undergo a consent discussion for participation in the overall study using a verbal information sheet. On or prior to the visit, a study team member may send a copy of the verbal information sheet via mail or email with the patient's permission. As part of the consent process, the study team member will provide a complete description of the study in clear and easy-to-understand language, including risks and benefits, as well as answer any questions that participants may have after receiving this information. If an eligible participant verbally consents to participate in the study, they will accrue.

All accrued participants will receive a copy of the information sheet via email or mail. Participants will be asked to schedule a time to complete the baseline visit and study staff will confirm their mailing address to send study materials, including instructions for downloading the Messy Memories app, tips for using the Messy Memories app, and mental health resources including study phone numbers to contact study staff. Study phone messages will be checked on a regular basis. Study materials may also be emailed to participants if needed or requested.

Study Visits:

Please note that study staff may email participants to schedule/confirm study visits, send study materials as needed or requested, and/or email questionnaires via Qualtrics. Study staff may also communicate with participants via SMS text messaging using CUIMC-encrypted cell phones available exclusively to study staff to schedule/confirm study visits and/or answer questions should they arise.

“Visit 1”/Baseline Visit (Approximately 60 Minutes): Participants will complete a brief baseline visit via Zoom (or over the phone if preferred). This session (guided by study staff) entails:

1. completing a brief baseline assessment, which will include:
 - a. details of the prior ICU admission (e.g., date, location)
 - b. comorbid medical and/or psychiatric conditions
 - c. psychological symptoms (PHQ-8, GAD-7, ASI)
 - d. health behaviors (IPAQ, PSQI, tobacco/alcohol use)
 - e. post-ICU support (see *Measures* for full description)
2. downloading the Messy Memories app to their smartphone and logging in with their study-provided login

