- a. Participants will be advised to reach out to the study team if they forget their login.
3. a brief orientation to the app with suggested guidance for usage

Participant App Usage: Participants will be asked to use the Messy Memories app for 6 weeks beginning the day that all components of the Baseline Visit are complete. This date marks the start of the intervention. Participants will be advised of the date which marks the end of the intervention (6 weeks later). They will be asked to focus on their memory of their ICU experience for memory processing. They will be asked to use the app at least 3 days a week for at least 30 minutes each day. They will be instructed to stop using and delete the app from their phones when their study participation ends.

Post-Baseline Check-In: Participants will receive a phone call from study staff within one week of the baseline assessment to confirm that they are not experiencing any technical difficulties with the app. If a participant expresses distress related (or not related) to the app, study staff will follow safety protocol by sharing the IRB-approved list of resources with the participant over the phone and/or via email and will consult with the study PI.

“Visit 2”/3-Week/Mid-Intervention Questionnaire (Approximately 25 minutes): Approximately three weeks after the start of the intervention (Baseline Visit) participants will be asked to complete a questionnaire by telephone or video consisting of the PCL-5, PHQ-8, GAD-7, ASI, IPAQ, and PSQI. If a participant expresses that they will not be available to complete the questionnaire by telephone or video, or if the study team is unable to reach the participant, the study team will send the questionnaire to the participant via Qualtrics. Those who do not complete the survey will remain on the study, and this task will be listed as “not completed” and included as part of analysis.

6-Week/End of Intervention Call: A member of the study team will call the participant within one week prior to the end of the intervention to remind the participant of the date when the intervention ends and that they are to stop using the Messy Memories app at that time. This call can also be used to schedule the 6-week/Post-Intervention Questionnaire.

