“Visit 3”/6-Week/Post-Intervention Questionnaire (Approximately 40 minutes): Approximately six weeks after the start of the intervention (Baseline Visit) participants will be asked to complete another questionnaire by telephone or video consisting of the PCL-5, PHQ-8, GAD-7, ASI, IPAQ, PSQI, substance use measures, implementation measures (e.g., feasibility, acceptability, appropriateness, satisfaction), and qualitative feedback on the intervention (e.g., likes, dislikes, suggestions for improvement). If a participant expresses that they will not be available to complete the questionnaire by telephone or video, or if the study team is unable to reach the participant, the study team will send the questionnaire to the participant via Qualtrics. Those who do not complete the survey will remain on the study, and this task will be listed as “not completed” and included as part of analysis.

“Visit 4”/12-Week/Follow-Up Questionnaire (Approximately 30 minutes): Approximately six weeks after the end of the intervention, participants will be asked to complete one final questionnaire by phone consisting of the PCL-5, PHQ-8, GAD-7, ASI, IPAQ, PSQI, and substance use measures. If a participant expresses that they will not be available to complete the questionnaire by telephone or video, or if the study team is unable to reach the participant, the study team will send the questionnaire to the participant via Qualtrics. Those who do not complete the survey will remain on the study, and this task will be listed as “not completed” and included as part of analysis.

Compensation:

Participants will be compensated a total of \$120 if they complete all components of the study in the form of TruCentive electronic gift cards. This compensation will be allocated in the following amounts:

- \$30 for completion of all components of the Baseline Visit (completing questionnaires, downloading the app, and being onboarded to the app with study staff)
- \$30 for completion of the 3-Week/Mid-Intervention Questionnaire
- \$30 for completion of the 6-Week/Post-Intervention Questionnaire
- \$30 for completion of the 12-Week/Follow-up Questionnaire

Participants who complete only part of a questionnaire (50%, for example) will *not* receive partial compensation for that questionnaire. Participants may, however, skip any question(s) that they do not feel comfortable answering, and this will not impact their compensation for the study.

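### Exploratory Aim 3 rests on Cohen's d with no confidence interval, and its pre-post t-test leaves the scheduled Week 3 and Week 12 PCL-5 scores unused when Week 6 is missing

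*Combined protocol and SAP*

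**What the plan says.** Section 3, Statistical approach for Aim 3, assesses target engagement by "comparing pre-/post-intervention change in PCL-5 score using one-sample t-tests with comparison values of 0". It then says "we will focus the interpretation of these analyses on effect sizes", names Cohen's d, and sets significance aside. Neither there nor elsewhere does the document plan a confidence interval. Section 3 also selects a minimum of 30 participants with no power calculation.

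The PCL-5 schedule is spread over several places:

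- Section 2, Intervention: "Mechanistic target and clinical symptom assessments will occur at Week 0 (baseline"), and again at Weeks 3, 6 and 12.
- Section 4, Screening: "Potential participants will also be asked to complete the PCL-5 as part of the screening questionnaire". A score of at least 10 is needed to enter.
- Section 4, Baseline Visit: the symptom item reads "psychological symptoms (PHQ-8, GAD-7, ASI"). The PCL-5 is not in the list.
- Section 4, Visits 2 and 3: the PCL-5 is in both questionnaires. Visit 3 carries the label "6-Week/Post-Intervention Questionnaire (Approximately 40 minutes").
- Section 4, Visit 4: "participants will be asked to complete one final questionnaire by phone consisting of the PCL-5", among other measures.

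On missed questionnaires, Section 4 says "Those who do not complete the survey will remain on the study, and this task will be listed as" not completed and enters the analysis. It gives no method for the missing PCL-5 score.

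**The concern.** Once significance is set aside, d is the only quantity being interpreted, and nothing planned shows its uncertainty. With about 30 people that uncertainty is wide.

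The second issue is who contributes. A one-sample t-test of change to Week 6 drops anyone without a Week 6 score, including people whose Week 3 score shows how they were doing. If loss is related to early change, the people left are a selected group and the mean change is biased. Aim 3 carries a stated hypothesis of improvement, and Section 3, General approach, plans to use this pilot's standard deviations and attrition to size the next trial. The estimate and its SD are therefore worth reporting well.

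A smaller matter is that the pre score is not identified. Screening collects a PCL-5, Section 2 promises one at Week 0, and the baseline list omits it.

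**Working it through.** **No plan figure to reproduce.** The plan gives no effect size, SD, alpha or power for Aim 3. From the documents come n=30, the visit schedule and the 70% retention benchmark (0.70 x 30 = 21 pairs). Everything else below is assumed.

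**1. Interval for d.** Take d as mean change over SD of change, so t = d x sqrt(n) with n-1 degrees of freedom. Inverting the noncentral t gives these two-sided 95% limits:

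| Observed d | n=30 | n=21 |
|---|---|---|
| 0.3 | -0.07 to 0.66 | -0.14 to 0.73 |
| 0.5 | 0.12 to 0.88 | 0.04 to 0.95 |

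Check for d=0.5, n=30: 1.96 x sqrt(1/30 + 0.25/60) = 0.38, a half-width that matches.

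**2. When complete pairs mislead.** Assume SD 14 at every visit, true change -5, and correlations pre-W3 0.70, pre-W6 0.65, W3-W6 0.75.

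- SD of Week 3 change = 14 x sqrt(2 x 0.30) = 10.84.
- Covariance of Week 3 change with Week 6 change = 196 x (0.75 - 0.70 - 0.65 + 1) = 78.4. Week 6 change therefore moves 78.4/10.84 = 7.23 points per SD of Week 3 change.
- Covariance of the Week 3 score with Week 6 change = 196 x (0.75 - 0.70) = 9.8, which is 9.8/14 = 0.70 points per SD.

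With 30% loss following a logistic curve of slope 0.5, 1 or 1.5 per SD, the mean of the driving variable among those retained shifts by -0.143, -0.253 or -0.327 SD (numerical integration). For loss on Week 3 change the complete-pair mean is -5 - 7.23 x (0.143, 0.253, 0.327) = -6.03, -6.83, -7.36. For loss on the Week 3 score it is -5 - 0.70 x (same) = -5.10, -5.18, -5.23. The mechanism decides the bias.

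**3. Simulation against a repeated-measures model.** n=30, 4,000 trials per scenario; further correlations pre-W12 0.60, W3-W12 0.68, W6-W12 0.75; Week 12 missing for 70% of those lost at Week 6 and 10% of others. The model has four visits, unstructured covariance and maximum likelihood. The true value is -5. Triplets are slopes 0.5 / 1 / 1.5.

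| Loss at Week 6 driven by | Complete pairs (coverage) | Model (coverage) |
|---|---|---|
| Poor Week 3 change | -6.02 / -6.85 / -7.35 (92.9 / 89.3 / 84.8%) | -5.01 / -5.03 / -5.02 (94.2 / 93.5 / 93.6%) |
| Good Week 3 change (slope -1) | -3.14 (89.5%) | -4.99 (93.7%) |
| Week 3 score | -5.10 / -5.20 / -5.26 (95.8 / 95.4 / 95.3%) | -5.00 / -5.02 / -5.03 (95.3 / 94.3 / 93.6%) |
| Chance | -5.02 (SE 2.62) | -5.03 (SE 2.43) |

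**4. Where the model falls short.**

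- Loss driven by the unseen Week 6 change (1,000 trials): model -5.93 / -6.73 / -7.25, complete pairs -6.79 / -7.96 / -8.78.
- Poor Week 3 change drives loss and half of those lost also lack Week 3: model -5.27 / -5.42 / -5.60. If all of them lack Weeks 3 and 12: -5.74 / -6.37 / -6.82.
- Compound symmetry in place of unstructured covariance (3,000 trials): -5.27 / -5.46 / -5.57 under poor Week 3 change, and -4.60 if improvers leave.
- Under the strongest change-related loss the model's SE is 2.53 against 2.41 for complete pairs.

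Intervals used t with pairs minus 1 degrees of freedom. Kenward-Roger itself was not simulated.

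**5. Regression to the mean if screening is the pre score.** Expected spurious change = -(1 - r) x SD x h, where h is the normal density over the upper tail at the cutoff of 10. With SD 14, an unselected mean of 10 gives h = 0.798 and a mean of 20 gives h = 0.405. The range runs from -(0.20 x 14 x 0.405) = -1.1 (r=0.8, mean 20) to -(0.35 x 14 x 0.798) = -3.9 (r=0.65, mean 10), with no treatment effect at all.

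**The case against.** The strongest reply is that the plan already discounts this result. Section 3, General approach, calls effect sizes from small pilots too imprecise for planning and does not intend to publish effect analyses. Aim 3 is labelled exploratory and no decision depends on d. All of that stands and limits the weight of the point. A reader might infer that the plan conceals its imprecision, but the General approach text says the opposite. What is missing is the interval itself.

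A reader might also infer that attrition is ignored. It is not. Every follow-up has a Qualtrics fallback, each questionnaire pays $30, and Section 3 compares consenting participants who did and did not complete the study. These reduce or describe loss. They do not say how a missing PCL-5 change is treated.

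The undefined standardiser is a minor point, since d from a one-sample test of change ordinarily uses the SD of change. The plural t-tests in Aim 3 leave room for tests at several visits. Week 6 as the post score is a reading of the Visit 3 label.

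On the model, the reply is that complete pairs do well under random or score-level loss, with coverage at least as good as the model's under score-level loss, and that every simulation input is assumed. Both are true, which is why the model belongs beside the complete-pair result.

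**Conclusion.** The point holds as an optional improvement to an exploratory analysis. Two things are firm on the text: no interval accompanies the one quantity interpreted, and the Week 3 and Week 12 PCL-5 scores have no stated role when Week 6 is missing. The interval widths follow from n alone once a value of d is supposed: 0.12 to 0.88 for d=0.5 at n=30.

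The bias is conditional. The documents give no loss mechanism, SD or correlation, so they do not support a claim that the Aim 3 result will be biased. The 30% loss is the plan's benchmark used as an assumption and is no forecast. Nor would it be right to say that a repeated-measures model removes the problem. It protects when loss depends on observed scores, and only partly when loss depends on the unseen Week 6 change or when Week 3 is missing too.

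The pre-score ambiguity is a wording matter, but its answer has consequences. If screening is the pre score, part of any observed fall is selection. Feasibility and acceptability, the primary outcomes, are untouched.

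**What to change.** In Section 3, Statistical approach for Aim 3:

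1. Name the contrast (pre to Week 6). Report mean PCL-5 change with its 95% CI, the SD of change and the number of pairs. Give d, defined as mean change over SD of change, with its 95% CI. Say that this analysis uses complete pairs only.
2. Beside it, show a likelihood-based repeated-measures estimate of the same change from all scheduled PCL-5 scores, with visit as a category and small-sample degrees of freedom.
3. State the limits: the model assumes data are missing at random; it reduces but does not remove bias if loss depends on the unseen Week 6 change; it helps little for people who also lack Week 3; and a compound-symmetry fallback protects only in part.
4. Name which PCL-5 is the pre score and reconcile Section 2 (Intervention) with Section 4 (Screening and Baseline Visit). If it is the screening score, note that selection at 10 or more brings regression to the mean, which neither the interval nor the model corrects.

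If only the minimum is done, items 1 and 4 are the ones to keep. The cost is a few sentences and slightly more analysis of scores already scheduled, with no added visits or participants. The price of item 2 is reliance on missing at random.

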Overall approach: The proposed pilot study will conduct preliminary testing of a novel mobile application (*Messy Memories*) that uses remotely delivered exposure therapy to reduce psychological distress and improve health behaviors in survivors of critical illness. Specifically, we aim to assess the feasibility and acceptability of recruiting and engaging critical illness survivors in the intervention. We also aim to explore the efficacy of the intervention in engaging the mechanistic target (PTSD symptoms) to reduce psychological distress. The results of this initial pilot study will be used to make refinements to the research protocol in preparation for a future adequately powered randomized controlled trial testing whether the intervention can significantly reduce psychological distress and, in turn, improve behavioral outcomes (e.g., medication adherence, physical activity, dietary habits, sleep patterns, substance use) among survivors of critical illness.

Eligibility:

Patients will be included if they meet the following inclusion/exclusion criteria:

Inclusion Criteria:

- (1) Age 18 years old or older

- (2) Able to speak and write in English
- (3) Previously admitted to an ICU
- (4) Have internet access (e.g., Wi-Fi)
- (5) Have access to an internet-equipped smartphone device (e.g., iPhone, Android)
- (6) Meet a minimum threshold of psychological distress related to their prior critical illness as demonstrated by scoring ≥ 10 points on the PTSD Checklist for the Diagnostic and Statistical Manual of Mental Disorders, 5th Edition (PCL-5, see *Measures* section for a complete description).

Exclusion Criteria:

- (1) ICU discharge occurred < 30 days prior to the time of study enrollment
- (2) Score < 10 points on the PCL-5 during the initial eligibility screening
- (3) Unable to comply with the protocol (either self-selected or indicating that s/he/they cannot complete all requested tasks) for reasons that include, but are not limited to, cognitive impairment (e.g., dementia), alcohol and/or substance abuse, or severe mental illness (e.g., schizophrenia).
- (4) Unavailable for follow-up for reasons such as terminal illness and imminent plans to leave the United States (as we have migrant or mobile patients due to their citizenship and work issues).

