Proctor's Implementation Measures: Three validated measures (Acceptability of Intervention Measure [AIM], Feasibility of Intervention Measure [FIM], and Intervention Appropriateness Measure [IAM]) will be used to assess the acceptability, feasibility, and appropriateness of the *Messy Memories* intervention, respectively.⁵⁶ Each measure consists of four items answered on a 5-point scale (1 = *strongly disagree*, 5 = *strongly agree*). Average responses of ≥ 4 on the AIM, FIM, and IAM are indicative of adequate acceptability, feasibility, and appropriateness, respectively.^{56,57}

System Usability Scale (SUS): The SUS is a reliable tool for evaluating the usability of various products and services, including hardware, software, mobile devices, websites, and applications.^{58,59} It consists of ten items answered on a 5-point scale (1 = *strongly disagree*, 5 = *strongly agree*). We will use a score ≥ 68 to indicate adequate usability, in accordance with prior studies.⁶⁰

PTSD symptoms: PTSD symptoms triggered by the prior critical illness and ICU hospitalization will be assessed using the PTSD Checklist for the Diagnostic and Statistical Manual of Mental Disorders, 5th Edition (PCL-5).⁶¹ The PCL-5 is an extensively validated self-report measure developed by the National Center for PTSD that corresponds to DSM-5 criteria for PTSD. Patients are provided a list of 20 PTSD symptoms and asked to rate how much they have been bothered by each symptom due to their prior critical illness and ICU hospitalization on a scale of 0 = *not at all* to 4 = *extremely*. We will classify participants with PCL-5 scores ≥ 34 as having elevated PTSD symptoms, which has been validated as a screening cutoff and used in prior studies of civilian populations.⁶²⁻⁶⁴

Other psychological symptoms: In addition to PTSD symptoms, we will also assess for symptoms of depression, anxiety, and anxiety sensitivity. Depression will be assessed using the 8-item Patient Health Questionnaire (PHQ-8),⁶⁵ with scores ≥ 10 positive for depression.^{66,67} Anxiety will be assessed using the 7-item Generalized Anxiety Disorder (GAD-7) scale,⁶⁸ with scores ≥ 10 positive for anxiety.⁶⁹ Anxiety sensitivity will be assessed using the 16-item Anxiety Sensitivity Index (ASI),⁷⁰ with scores ≥ 17 indicating high anxiety sensitivity.⁷¹

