Health behaviors: The International Physical Activity Questionnaire (IPAQ),⁷² will be used to measure the type, frequency, and intensity of daily physical activity. The Pittsburgh Sleep Quality Index (PSQI)⁷³ will be used to measure total sleep duration and sleep quality. Participants will also be asked to report on their patterns of tobacco, alcohol, and substance/drug use.

Post-ICU support: As part of the baseline visit, participants will be asked questions about any medical, psychological, and social support that they may have received after their prior ICU admission. Participants will also be asked about what forms of post-ICU support they think would be helpful for patients and their families.

Sociodemographic and clinical characteristics: Participant sociodemographic information (e.g., age, sex, gender, sexual orientation, race, ethnicity, primary language, educational attainment, occupation, annual household income, marital/partner status, living situation, insurance status) will be self-reported at screening. Participants will also be asked to self-report any comorbid medical or psychiatric conditions, as well as provide information about their prior ICU admission (e.g., location, primary diagnosis, duration of hospitalization, need for intubation/mechanical ventilation, need for renal replacement therapy, need for central line placement).

3. Statistical Procedures

General approach: Given that this pilot study is, by design, not powered to test the effect of our intervention on study outcomes, we do not intend to publish analyses of these effects. Although some have used pilot studies to estimate effect sizes on primary outcomes, we agree with leaders in our field who argue that effect size estimates from small pilot studies are too imprecise to meaningfully inform effect size assumptions or power analyses for larger, later-stage studies. Therefore, we do not provide power calculations for the effects of our intervention on study outcomes. However, we will use estimates from these studies (e.g., standard deviations, attrition rates) to help determine appropriate sample sizes for a future study that is powered to detect meaningful reductions in measures of psychological distress following critical illness.

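### The Week 0 PCL-5 is missing from the itemised Baseline Visit and Aim 3 never says which score is 'pre'; defaulting to the screening score biases the change toward improvement

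*Combined protocol and SAP*

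**What the plan says.** **Schedule.** Section 2, Intervention: "Mechanistic target and clinical symptom assessments will occur at Week 0 (baseline"), then Weeks 3, 6 and 12. Aims 1 to 3 and Section 3 identify the mechanistic target as PTSD symptoms and measure it with the PCL-5.

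**Baseline Visit.** Section 4, Visit 1, item 1c lists "psychological symptoms (PHQ-8, GAD-7, ASI"). Those are the instruments that Section 2, Measures, treats as additional to the PTSD measure: "In addition to PTSD symptoms, we will also assess for symptoms of depression, anxiety, and anxiety sensitivity". The Week 3, Week 6 and Week 12 lists in Section 4 each name the PCL-5 first.

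**Screening.** Section 4, Screening, asks candidates to "complete the PCL-5 as part of the screening questionnaire (scores ≥ 10 points are required for study eligibility"). The matching exclusion criterion in Section 2 is "Score < 10 points on the PCL-5 during the initial eligibility screening".

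**Analysis.** Section 3, Aim 3, plans on "comparing pre-/post-intervention change in PCL-5 score using one-sample t-tests with comparison values of 0", with interpretation resting on Cohen's D rather than significance. Neither 'pre' nor 'post' is attached to a visit there, in the Outcomes paragraph or in the Aims.

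**The concern.** Two parts of the protocol disagree on whether the target measure is taken at Week 0, and the analysis section does not settle it. Staff work from the visit list. If they follow it, the only PCL-5 before app use is the screening score, which has two defects as a baseline.

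- It is the score on which people were selected. Anyone whose score was high by chance on that day is more likely to get in and will tend to score lower next time, with or without the app.
- It is not taken at the start of the intervention. A separately scheduled consent visit and then a separately scheduled Baseline Visit follow it, and no maximum interval is set. Any drift in that gap is credited to the app. Screening may also be self-completed online, whereas follow-up is by telephone or video first.

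There is no control arm to absorb either effect. The bias falls on Cohen's D, the quantity the plan says it will read as a possible signal.

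**Working it through.** **1. Text comparison.**

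| Time | PCL-5 named in the procedures? |
|---|---|
| Screening | Yes, and used for selection |
| Baseline Visit (Week 0) | No |
| Week 3 | Yes |
| Week 6 | Yes |
| Week 12 | Yes |

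The visit that the schedule calls baseline is the only post-consent assessment whose list lacks the target measure.

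**2. Inputs for the size.** From the documents: selection at 10 or more; 20 items scored 0 to 4, so a range of 0 to 80; minimum n = 30. The plan has no power or effect-size figure to reproduce and gives no PCL-5 distribution. Assumed: mean in the screened pool 10 to 30, SD 12 to 17, correlation r between screening and Week 6 of 0.7 to 0.9, and no true change.

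**3. Closed form (normal scores, no bounds).** With a = (10 − mean)/SD and λ = φ(a)/(1 − Φ(a)), the expected change from screening is −(1 − r) × SD × λ. At mean 20, SD 15, r = 0.8:
- a = −0.667 and λ = 0.319/0.748 = 0.427
- expected change = −0.2 × 15 × 0.427 = −1.28 points
- variance of change = (1 − r)² × SD² × (1 + aλ − λ²) + SD² × (1 − r²) = 4.8 + 81 = 85.8, so SD of change = 9.3
- d = 1.28/9.3 = 0.14

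**4. Simulation with rounded scores clipped to 0–80.** Three score models were run, because skew alters the size: normal; gamma true score plus normal error; and gamma scores joined by a Gaussian copula. Midpoint results:

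| Model | Spurious fall (points) | d |
|---|---|---|
| Gamma, copula | 0.9 | 0.08 |
| Normal | 1.2 | 0.13 |
| Gamma true score + error | 1.6 | 0.18 |

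Range over all three models, SD 12/15/17 and r 0.7/0.8/0.9 (135 cells in all). The mean is the nominal value before clipping:

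| Screened mean | Share scoring ≥ 10 | Fall (points) | d |
|---|---|---|---|
| 10 | 30–52% | 0.9–6.0 | 0.14–0.43 |
| 15 | 49–68% | 0.6–3.7 | 0.09–0.32 |
| 20 | 68–82% | 0.2–2.7 | 0.04–0.22 |
| 25 | 82–94% | 0.1–1.9 | 0.01–0.15 |
| 30 | 89–99% | 0.0–1.2 | below 0.10 |

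The direction was toward improvement in every cell.

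**5. Scale.** The 95% half-width on d at n = 30 is 1.96 × √(1/30 + d²/60) ≈ 0.36. The midpoint bias is therefore 0.08/0.36 = 22% to 0.18/0.36 = 50% of the sampling error. If a two-sided 0.05 test is assumed (the plan states no level), a study with no effect would show significant improvement in 6% to 16% of repeats at the midpoint instead of 2.5%. This is secondary, because the plan does not rest on significance.

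**6. What a separate Week 0 score removes.** With independent measurement errors the residual is zero points in every cell. If screening and Week 0 share error, the normal model leaves a fraction (r_sb − r)/(1 − r), where r_sb is the screening-to-Week 0 correlation. With r = 0.8:
- r_sb = 0.85 leaves 0.05/0.20 = 25%
- r_sb = 0.90 leaves 0.10/0.20 = 50%
- r_sb = 0.95 leaves 0.15/0.20 = 75%

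Drift between screening and Week 0 and the mode difference cannot be sized from the documents and are not included.

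**The case against.** **The omission may be a drafting slip.** The Baseline Visit list is introduced by wording that need not be exhaustive. Item 1d is also shorter than the Measures section, which covers "patterns of tobacco, alcohol, and substance/drug use". This stands: a Week 0 PCL-5 is not ruled out, and the harm arises only if the schedule is not followed. But no part of the procedures describes its collection, and 'pre' stays undefined either way.

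**Screening may be meant to serve as Week 0.** Sociodemographic data are taken at screening and not repeated, and item 1c would then list just the symptom scales not yet given. This is a fair reading, though nowhere stated. It does not remove the problem, because it makes the selected score the baseline by design.

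**The size is assumed and may be small.** This is correct. The largest values need a pool in which roughly half or more of those screened fall below 10. Some recruitment sources, such as support groups, are likely to score higher; others, such as the health-record list, are not selected for distress.

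**Repeating the PCL-5 may remove little.** This is true if the two visits are close together and their errors are highly correlated, as the 0.95 case shows. Even then it removes part of the bias, and it removes any drift before Week 0.

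**Little hangs on Aim 3.** It is exploratory, and of intervention effects Section 3 says "we do not intend to publish analyses of these effects". This limits the severity. The plan still intends to read Cohen's D for signals of effect.

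**Conclusion.** The concern holds. The schedule and the itemised Baseline Visit disagree about the PCL-5 at Week 0, and the Aim 3 'pre' value is undefined. Confidence in the omission and in the direction of the bias is high. Whether the bias occurs depends on what staff do at Week 0. Its size depends on the assumed distribution: d of 0.08 to 0.18 at the midpoint, up to 0.43 if the screened mean is near 10, and negligible if it is near 30. The primary feasibility and acceptability outcomes are untouched. It should be fixed because the edit is small and the missing measurement cannot be obtained afterwards.

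**What to change.** - **Section 4, Visit 1, item 1c:** add the PCL-5, completed before the app is downloaded, so that the list agrees with the Week 0 schedule in Section 2.
- **Section 3, Aim 3:** define 'pre' as the Week 0 PCL-5 and 'post' as the Week 6 Post-Intervention score. State that the screening score is used for eligibility only.
- **Limitations:** say that natural recovery after Week 0 is not removed without a control arm, and that error shared between screening and Week 0 leaves some regression to the mean.
- **Fallback for participants without a Week 0 score:** state that screening is 'pre', report the interval from screening to app start, and give Cohen's D beside an expected regression-to-the-mean shift with its assumptions. This settles the definition but does not remove the bias.

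The cost is one 20-item questionnaire within a visit planned at about 60 minutes, so a few more minutes of participant burden, plus a short edit to Aim 3.
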